12.1 Risks

Blood draws

Blood draw by venipuncture for HbA1c at Baseline, month 3, and month 6 is a standard care procedure which would occur regardless of participation in this study. Blood draws may cause discomfort and bruising at the puncture site. Participants may also experience lightheadedness or fainting during the blood draw and there is a slight risk of infection. The total blood volume needed for each HbA1c test is less than 5 mL.

Capillary (fingerstick) blood glucose and ketone testing

BGM by fingerstick is a standard care procedure for PWD. Participants will follow Virta's usual frequency recommendations for BGM. Fingerstick ketone monitoring is a routine procedure for Virta participants and uses the same technique as BGM. Study subjects will be asked to monitor and log fingerstick ketones twice daily; this is more than Virta's usual recommendation of once daily. Risks arising from

fingerstick testing are minimal and may include pain, bruising, or the infrequent occurrence of skin infection.

CGM use

CGM use is a routine part of the care for many PWD. CGM users usually report less pain or discomfort with CGM than with capillary blood glucose testing. Mild pain on insertion of CGM may be experienced by subjects at low frequency. Known allergies to medical grade adhesives is an exclusion from participation. Cutaneous complications of CGM use are typically wear-related erythema, itching, and induration. The incidence of these complications is expected to be low, 0.13 to 0.15 events per week of wear-time, with the majority (79%) being mild. Study discontinuation rate due to skin reactions is expected to be very low.²⁴

Privacy

The study requires use of web-based applications, which include providing personal information and personal health information. There is always some risk that data will be compromised, and that personal information will become available to unexpected parties. Several mechanisms are in place to protect personal information, including use of de-identified participant identification (ID) numbers whenever possible.

Surveys

Surveys will be used to collect information on food intake and other PROs. Sometimes survey questions can trigger uncomfortable feelings. Participants will be informed that they are not required to respond to questions that make them uncomfortable for whatever reason.

12.2 Potential Benefits

Participants in both arms of the study may benefit from the additional monitoring they are requested to complete as part of the study. For example, this study requests two blood ketone tests per day for 6-7 months, which is more than what participants are requested to do in the usual Virta Treatment. The additional monitoring information collected may be useful for helping participants and providers manage diabetes care.

Participants assigned to the CGM arm may benefit from access to continuous glucose data and the use of the FreeStyle Libre 2 app. Use of FreeStyle Libre 2 and the associated app may aid in a better understanding of which foods and behaviors keep glucose and ketones in target ranges.

Additionally, information from this study could lead to new and more effective methods for helping people with T2D manage their glucose and diabetes or adhere to nutrition therapies.

12.3 Analysis of Risks in Relation to Benefits

In this study, risks posed beyond standard care are minimal. The rationale for exposing study participants to the minor risks associated with blood draws, capillary glucose and blood ketone testing, and CGM use, is that these components of usual diabetes care are outweighed by the potential benefit

to patients if this study can help define whether method of glucose testing may impact health-outcomes.

13 Assessment of Safety and Data Safety Monitoring Plan (DSMP)

13.1 Definitions

The following definitions will be used in the assessment of safety:

Adverse Event (AE) is any unfavorable and unintended sign (including an abnormal laboratory finding), symptom or disease temporally associated with the intervention, regardless of whether it is considered related to the intervention.

Serious Adverse Event (SAE) is any adverse event that

- (1) results in death;
- (2) is life-threatening;
- (3) results in inpatient hospitalization or prolongation of existing hospitalization;
- (4) results in a persistent or significant disability/incapacity;
- (5) results in a congenital anomaly/birth defect; or
- (6) based upon appropriate medical judgment, may jeopardize the participant's health and may require medical or surgical intervention to prevent one of the other outcomes listed in this definition.

Life-threatening means the event places the subject at immediate risk of death from the event as it occurred.

Unanticipated Event (UAE) is defined as an event, experience or outcome that meets **all three** of the following criteria:

- is unexpected; AND
- is related or possibly related to participation in the research; AND
- suggests that the research places subjects or others at a greater risk of harm (including physical, psychological, economic, or social harm) than was previously known or recognized.

Unexpected means the nature, severity, or frequency of the event is not consistent with either:

- the known or foreseeable risk of adverse events associated with the procedures involved in the research that are described in the protocol-related documents, such as the IRB-approved research protocol, the ICF, and/or other relevant sources of information, such as product labeling and package inserts
- the expected natural progression of any underlying disease, disorder, or condition for the participant experiencing the adverse event, and/or the participant's predisposing risk factor profile for the adverse event.

Unanticipated Problems Involving Risks to Subjects or Others (UPIRTSO) means:

- any problem or event which in the opinion of the Investigator was unanticipated, serious; AND
- at least possibly related to the research procedures

Possibly related means there is a reasonable possibility that the incident, experience, or outcome may have been caused by the procedures involved in the research.

Minimal risk means that the probability and magnitude of harm or discomfort anticipated in the research are not greater in and of themselves than those ordinarily encountered in daily life or during the performance of routine physical or psychological examinations or tests.

Severity of events will be defined as:

- **Mild** requires minimal or no treatment and does not interfere with the participant's daily activities.
- **Moderate** results in a low level of inconvenience or concern with therapeutic measures. Moderate events may cause some interference with the participant's functioning.
- **Severe** interrupts a participant's usual daily activity and may require systemic drug therapy or other treatment.

13.2 Safety Review

Risks described in section 12.1, AEs, SAEs, and UAEs will be monitored continuously throughout the study by study staff.

13.3 Reporting Plans

The delegated Investigator will report all reportable AEs, SAEs, UAEs, and UPIRTSOs to Advarra in accordance with IRB policies.

AE's are considered reportable if they meet any of the following:

- Severe sensor-related reactions or infections requiring in-person medical care
- Severe hypoglycemia defined as requiring assistance of another person due to altered consciousness, and requiring another person to actively administer carbohydrate, glucagon, or other resuscitative actions.
- Severe hyperglycemia if the event involves diabetic ketoacidosis (DKA) or hyperosmolar hyperglycemic state (HHS), as defined in Kitabchi et al.²⁵

Reportable AEs and all SAEs will be recorded within an adverse event log with a description including the nature of the event, the date and time of onset and/or frequency, determination of non-serious versus serious, intensity (mild, moderate, severe), duration of the event, relationship to the intervention, the expectedness, and outcome of the event.

This study does not include an independent monitoring committee (e.g., no Data Safety Monitoring Board). Since the study procedures are of minimal risk, SAEs are not expected. If any UAEs related to the research and involving risks to subjects or others happen during this study (including SAEs), they will be reported to the IRB in accordance with Advarra IRB standard operating procedure (SOP).

13.4 Stopping Rules and Study Suspension or Termination

This study will be stopped prior to completion if information becomes available during the study that indicates a stop, which may include information related to adverse events or the potential for adverse

events. The study may also be stopped prior to completion if recruitment challenges or retention issues will impact the ability to properly analyze defined endpoints or for other reasons determined by the Investigator.

14 Data Management and Record Keeping

Data for the study will be collected and documented: 1) verbally and electronically from participants by Virta and IDC staff, 2) in Virta's HIPAA compliant EMR and patient-facing app (the mobile interface where patients interact with the care team), 3) from the Libre Pro reader and LibreView website , 4) in REDCap, 5) via the web-based ASA24 and 6) in electronic files on secured, password protected institutional computers.

CGM-related data will either be uploaded directly from the blinded Libre Pro reader and then downloaded to an institutional computer or downloaded from the LibreView website (for participants assigned to the CGM arm). CGM data will be saved on password-protected computers, which are backed up to a secure server. Participants assigned to the CGM arm will need to create a personal account in order to access the phone-based app associated with the FreeStyle Libre 2 system. Data in the app is secure to the extent provided by the manufacturer.

Participant and study-related data will be entered into REDCap, a 21 CFR Part 11-compliant data capture system that is licensed to IDC. REDCap includes password protection and internal quality checks, including field validation to help identify inconsistent, incomplete, or inaccurate data. Data entered into REDCap will come directly from the original source data; or in some cases REDCap will serve as the source data (e.g. protocol deviations; tracking participant phone calls between participants and IDC staff; when participants respond to surveys directly in REDCap; etc.). REDCap maintains a built-in audit trail that logs all user activity and all pages viewed by every user, this includes entering data, exporting data, modifying a field, running a report, or add/modifying a user, etc.

Participants will complete surveys directly in REDCap and directly in ASA24. ASA24 is a free, web-based dietary assessment tool that is run by the National Institutes of Health. ASA24 data is associated with study ID and does not capture any personally identifiable information from participants. All completed surveys will be retained in the web-based server as a source document and will also be downloaded from the servers and stored as .CSV or similar files throughout the study.

This trial will be registered at ClinicalTrials.gov once the protocol has been approved by the IRB; trial results will be added to the ClinicalTrials.gov after study completion.

14.1 Data Monitoring

Investigators and study staff will periodically monitor data for completeness and quality as specified in data-sharing contracts and to provide the opportunity to address any concerns.

14.2 Confidentiality

Participants will be assigned a unique ID number at the time of enrollment. Whenever possible, participant records and datasets will contain the unique ID only. The participant will be informed during

the study screening process and via the ICF that their personal study-related data will be accessible by both Virta and the IDC throughout the duration of the study. Participant data and any related records may also be made accessible to regulatory authorities or as required by law.

The confidentiality of all participant information and data are protected to the extent allowed by law. Records will be kept confidential in accordance with HIPAA privacy regulations. Investigators and personnel will not use data or records for any purpose other than conducting the study; however, deidentified participant data may be used for educational purposes and shared in medical journals, at scientific meetings, or in similar settings. No identifiable data will be used for future study without first obtaining IRB approval. In the case a limited data set is needed for future study, a data use agreement will be utilized.

14.3 Records Retention

Clinical research records, including IRB records and records related to the study will be stored in a manner that ensures privacy, confidentiality, security, and accessibility when the clinical research is being conducted and after the study is completed. Based on regulatory requirements, Advarra will retain study records for at least 3 years after the last site reviewed by the IRB has terminated. Any hardcopy documents will be moved to the Advarra archive files at termination. After the record retention period has been met, all study-related materials are destroyed. Once a study is terminated in CIRBI (Center for IRB Intelligence), the study is automatically archived in the system for the retention period noted above. Prior to purging study documentation/information from CIRBI (i.e., studies that have met the retention period), CIRBI sends out an automated notification to the study contacts. The notification instructs the study contacts to log in to CIRBI and retrieve any documentation/information needed within 30 days of the notification. After the 30-day period, all documentation/information is purged from CIRBI.

All HIPAA-related documents containing PHI collected by the IDC, will be retained for at least six years after completion of the study. Physical documents will be consolidated and stored in boxes in a secure location after study completion and electronic documents will be maintained in designated research study folders on the institutional drive in accordance with the HealthPartners data retention guidelines.

15 Statistical Plan

15.1 Analysis of Primary Endpoint

Summary statistics (including number, mean, median, standard deviation, minimum and maximum) for percentage (%) of TIR (glucose 70 - 180 mg/dL), based on 14-day CGM assessments, will be calculated by treatment and period.

The primary endpoint will be analyzed using a linear mixed model with treatment (BGM or CGM), period (Baseline (period A) and Post-Dietary Change (period B)), and interaction between treatment and period as fixed effects, and patient as random effect. The model will be fitted to all the data simultaneously and from this model the relevant treatment differences will be estimated. Adjusted mean estimates for each treatment with standard errors, the adjusted estimate of treatment mean difference with standard error and a 95 % confidence interval for the treatment mean difference will be provided. The statistical test will be two-sided tests at a nominal 5% significance level.

Enrolled participants without adequate Baseline blinded Libre Pro CGM data will not be included in the analysis. Adequate Baseline blinded CGM data is defined as a minimum of 5 days of sensor data. In cases where two blinded sensors are worn in the same contact period, sensor data may be combined.

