4.2.1 Primary Outcome Measures

Outcome	Assessment Method
Change in 14-day CGM-derived TIR (% of time with glucose 70-180 mg/dL) from Baseline to 3-month Post-Dietary Change period	See CGM-related outcome measures described above

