15.4 Study Hypotheses

Alternative primary hypothesis: CGM will lead to greater improvements in TIR at month three compared to BGM in people with T2D who participate in the Virta Treatment.

Alternative secondary hypotheses:

- CGM will lead to greater blood ketone levels at month three (a presumed marker of adherence to the Virta dietary plan) compared to BGM in people with T2D who participate in the Virta Treatment.
- CGM will lead to greater improvements in other glycemic markers at month three compared to BGM in people with T2D who participate in the Virta Treatment.

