15.5 Sample Size Determination

The sample size estimation is based on the following assumptions:

- 80% power (at 0.05 significance level) to test the primary hypothesis, which is the difference in TIR between BGM and CGM arms
- anticipated mean difference in TIR between CGM and BGM = 10%
- anticipated standard deviation of TIR in each arm = 20%

The two-sided t-test suggests N=63 for each arm. Assuming an 85% retention rate at the end of the 3-month Post-Dietary Change period brings the required sample size to approximately N=75 per arm; or N=150 randomized participants with adequate Baseline data.

Consented participants who are not randomized do not count toward the 150 total participants; these participants may be replaced.

16 Ethics/Protection of Human Subjects

This protocol and any amendments will be submitted to Advarra for formal approval of the study conduct. The decision of the IRB concerning the conduct of the study will be made in writing to the Investigator. A copy of the initial IRB approval letter will be provided to the study funder (Abbott Diabetes Care) before commencement of this study.

This study will be conducted in full accordance with all applicable Federal and state laws and regulations including 45 CFR, and the HIPAA Privacy Rule. Any episodes of non-compliance will be documented. The Investigators will perform the study in accordance with this protocol, will obtain consent, and will report unexpected problems in accordance with IRB policies and procedures. Collection, recording, and reporting of data will be accurate and will ensure the privacy, health, and welfare of research participants during and after the study.

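### The primary TIR model implies an unadjusted difference in change; a Baseline-adjusted Month 3 difference is more precise and uses data already required

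*Combined protocol and SAP*

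**What the plan says.** The primary outcome in Section 4.2.1 is "Change in 14-day CGM-derived TIR (% of time with glucose 70-180 mg/dL) from Baseline to 3-month Post-Dietary Change period". The hypothesis in Section 15.4 is that "CGM will lead to greater improvements in TIR at month three compared to BGM in people with T2D".

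Section 15.1 fits a "linear mixed model with treatment (BGM or CGM), period (Baseline (period A) and Post-Dietary Change (period B)), and interaction between treatment and period", with patient as a random effect. Baseline TIR therefore enters as a response. It is not a covariate, and the arm means at Baseline are not constrained to be equal. On what will be tested, the section says that "from this model the relevant treatment differences will be estimated" and promises an "adjusted estimate of treatment mean difference with standard error". It names no contrast. It also states: "Enrolled participants without adequate Baseline blinded Libre Pro CGM data will not be included in the analysis".

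Section 15.5 sizes the trial on the primary hypothesis, "which is the difference in TIR between BGM and CGM arms", with a 10-point effect and "anticipated standard deviation of TIR in each arm = 20" (percentage points). It gives no Baseline to Month 3 correlation. Section 15.2 applies the same model to the other continuous CGM metrics and to HbA1c.

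**The concern.** A change endpoint and a hypothesis about improvement point to the treatment-by-period interaction as the primary contrast. The model gives each arm its own Baseline mean, so with complete data that contrast is the raw difference in mean change. It subtracts the whole Baseline value, whatever the correlation. With equal SDs, this beats a Month 3-only comparison when ρ exceeds 0.5 and loses to it when ρ is below 0.5. It is less efficient than an adjusted analysis at any ρ below 1.

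The promise of a treatment mean difference in 15.1, and the wording of 15.5, leave room for the Month 3 (period B) arm difference instead. That contrast is also less efficient than the adjusted one whenever ρ is above 0.

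What is at stake is power and interval width for the primary result and for the continuous secondary endpoints. Bias and type I error are not at issue.

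**Working it through.** **Inputs from the documents.** Difference 10, SD 20, two-sided 5%, 80% power, 63 evaluable per arm, 85% retention, 75 randomised per arm (15.5); 1:1 allocation (7.2).

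**Assumptions not in the documents.** ρ from 0.3 to 0.7; equal SDs at Baseline and Month 3.

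**1. The plan's own figure.** The normal-approximation formula gives n = 2(1.96 + 0.84)² × 20²/10², which rounds up to 63 per arm. The exact noncentral t gives 79.5% power at 63 and 80.1% at 64. For retention, 63/0.85 = 74.1, hence 75. The stated sizes reproduce.

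**2. What the interaction estimates.** In a simulated complete data set, the fitted interaction and the raw difference in mean change agreed (10.302 and 10.302; SE 3.380 and 3.380).

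**3. Formulas, with 20 as the SD of TIR at each time.**
- Interaction: SD of change = 20√(2(1−ρ)), 124 df.
- Adjusted: residual SD = 20√(1−ρ²), 123 df.
- SE = SD × √(2/63); power from the noncentral t with noncentrality 10/SE.
- Variance ratio, adjusted to interaction: (1−ρ²)/(2(1−ρ)) = (1+ρ)/2.

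At ρ = 0.5, for example, the SD of change is 20.0, SE 3.56 and power 79.5%. The adjusted SD is 17.3, SE 3.09 and power 90%.

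| ρ | SD change | SD adjusted | Power, interaction | Power, adjusted | 95% CI half-width, interaction | 95% CI half-width, adjusted | CI narrower by |
|---|---|---|---|---|---|---|---|
| 0.3 | 23.7 | 19.1 | 65% | 83% | 8.3 | 6.7 | 19% |
| 0.4 | 21.9 | 18.3 | 72% | 86% | 7.7 | 6.5 | 16% |
| 0.5 | 20.0 | 17.3 | 79.5% | 90% | 7.1 | 6.1 | 13% |
| 0.6 | 17.9 | 16.0 | 88% | 94% | 6.3 | 5.6 | 11% |
| 0.7 | 15.5 | 14.3 | 95% | 97% | 5.5 | 5.0 | 8% |

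A Month 3-only comparison has 79.5% power at every ρ. The last column is 1 − √((1+ρ)/2). It is scale-free, so it applies to the 15.2 metrics at the same ρ.

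**4. If 20 is the SD of change.** The interaction has 79.5% power at every ρ. The adjusted SD is 20√((1+ρ)/2) = 16.1/16.7/17.3/17.9/18.4, giving 93/91/90/88/86% power at ρ = 0.3/0.4/0.5/0.6/0.7.

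**5. If the period B difference is meant, with dropout.** Generalised least squares with 75 Baseline and 63 Month 3 values per arm, SD 20, at the same five ρ values:
- Period B difference: SE 3.54/3.52/3.49/3.46/3.42, power 80.1/80.5/81.1/81.8/82.7%.
- Interaction: SE 4.10/3.81/3.49/3.14/2.73, power 68/74/81/89/95%.
- Common-baseline model: SE 3.40/3.27/3.09/2.85/2.54, power 83/86/90/94/97%.

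Keeping Baseline-only participants in the planned model does not close the gap.

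**6. Unequal SDs.** With Baseline SD0 and Month 3 SD3, var(change) − var(adjusted) = (SD0² + SD3² − 2ρ·SD0·SD3) − SD3²(1−ρ²) = (SD0 − ρ·SD3)², which is never negative. The two tie only when ρ = SD0/SD3. This is a large-sample result.

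**7. Simulation** (20,000 trials per ρ, complete data, same five ρ values). Interaction power was 65.8/71.6/79.8/87.6/94.8%; ANCOVA power was 82.9/85.6/89.9/93.2/97.1%. Type I error was 4.9 to 5.4% for both.

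**The case against.** The strongest reply is that nothing here is wrong. The planned test is valid, it uses Baseline, it matches the change endpoint, the sample size reproduces, and the study calls itself non-pivotal. Choosing between two valid estimators could be called preference.

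The benefit also rests on a correlation the documents do not give. Against the interaction, with 20 as the SD of TIR, it is 18 power points at ρ = 0.3 but only about 2 at 0.7. At 0.8 the powers are 99.3% and 99.6%. If the period B difference was intended, the pattern reverses: the gain is only about 3 points at ρ = 0.3 and grows with ρ. All of this stands, and it limits how large a gain can be claimed. It does not change the direction under either reading of the contrast or of the SD.

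Three smaller points also stand:
- The adjusted-SD formula leaves out chance Baseline imbalance. Allowing for it, ANCOVA power is 79.2% at ρ = 0, 89.3% at 0.5 and 93.4% at 0.6, a cost of about 0.3 points or less.
- The statistical plan is part of the protocol, so the change would be filed as an amendment (Section 16).
- Sections 7.2 and 8.4 allow randomisation after five days of recording while the Baseline sensor stays on, so part of Baseline can follow open-label assignment. That wear still precedes Day 0 and feeds the change score equally. It is a caveat on assuming a common Baseline mean, and it does not favour the unadjusted contrast.

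**Conclusion.** The point holds as a recommended improvement, not as an error in the plan. Under randomisation the adjusted and unadjusted contrasts estimate the same mean difference, so the endpoint need not change. For ρ between 0.3 and 0.7, adjustment gives a confidence interval 19% to 8% narrower than the interaction's when SDs are equal. Power is higher under every reading checked.

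The documents do not show that the trial is underpowered. If 20 is the SD of TIR, however, the interaction reaches the planned power only when ρ is about 0.5 or more. The adjusted analysis has roughly that power even at ρ = 0, so the design stops depending on an unstated quantity. The unnamed contrast and the unstated correlation are missing details that the same edit can supply.

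**What to change.** In 15.1, and in 15.2 for the continuous CGM metrics and HbA1c, make the Baseline-adjusted Month 3 arm difference the primary estimate. Either form will do:
- ANCOVA of the Month 3 value on arm and the Baseline value.
- A mixed model with period and an indicator equal to 1 only for the CGM arm at Month 3, no arm term at Baseline, and unstructured covariance.

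When everyone has a Baseline value, the two give the same point estimate. They agreed to three decimals in three simulated data sets with Month 3 values missing at random given Baseline. For HbA1c, the mixed model also keeps anyone lacking a Baseline value.

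In 15.5, state whether 20% is the SD of Month 3 TIR or of change. If the unadjusted contrast is kept, name it in 15.1 and give the assumed ρ or SD of change.

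The cost is statistical wording, model code and a protocol amendment, with no added patients, visits or data. It should be done before outcome data are seen, so that the adjustment is prespecified.
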